6.1 Subject accounting

The number and percentages of subjects in each analysis set as defined in Section 4 will be presented by dose level cohort.

6.2 Disposition and withdrawals

The number and percentage of subjects will be summarized by dose level cohort including:

- Subject status: not yet begun treatment (for reporting subject status while trial is ongoing), on treatment, discontinued trial treatment, and withdrawn from trial
- Primary reasons for discontinuation from trial treatment, and discontinuation from trial
- Total number of days on trial

7 Demographics and Background Characteristics

Demographic and baseline characteristics, as specified below, will be presented descriptively. The DPS will present further details on what categories are included in below summaries.

7.1 Demographics and baseline characteristics

The following demographic characteristics will be presented:

- Sex
- Age (years), as entered on the CRF, continuously and categorized as <65 and >/= 65 years
- Race and ethnic origin, as entered on the CRF
- Ethnicity
- Weight (kg) at baseline

7.2 Disease characteristics

The following disease diagnosis will be presented:

- Primary diagnosis at Screening (uterine, prostate, etc.)
- Time from initial diagnosis to 1st dose (years)

7.3 Prior Anti-Cancer Therapy

- The following Prior Anti-cancer therapy will be summarized: the number of prior anti-cancer therapies (One prior line, Two prior lines, Three prior lines, ≥3 prior lines, and Missing)
- Type of prior therapies (Platinum-based therapy, Anti-EGFR therapy, Anti-PD-1/PDL1 therapy, Systemic therapy, Prior Radiotherapy, Prior surgery related to the disease)
- Best response to last prior cancer therapy (as collected in eCRF; CR, PR, SD, PD, NE)

8 Exposure and Compliance

8.1 Dose Level Cohorts

All subjects receiving investigational treatment during this open-label trial will receive GEN1044. Subjects in the Escalation Part will receive dose levels as assigned.

8.2 Dosage and Treatment Duration

Descriptive statistics for the number of cycles initiated, duration of treatment (days), number of dose administrated, cumulative dose administered (mg), Number of full dose, and Cumulative full dose (mg) will be presented overall and by dose level cohort.

Subjects with dose interruptions, dose reduced, and delay as well as reasons for these modification (adverse event, drug administration issues, or other), will be summarized by dose level cohort.

9 Safety

9.1 Primary safety analysis

Dose-Limiting Toxicities (DLTs)

The primary endpoint for the Escalation Part of this trial is the DLTs. Adverse events (AEs) that are assessed by the investigator to be at least possibly related to GEN1044, which occur during the DLT period of the Escalation Part. DLT will be summarized by PT in order of descending frequency using Dose-Determining Analysis Set.

The distribution of DLT occurring at the dose level will be plotted by subjects.

9.2 Adverse events (AEs)

AEs will be coded using MedDRA, and the National Cancer Institute Common Terminology Criteria for AEs (CTCAE criteria v5.0). Subjects will be included only once in incidence summary tables, presented by Preferred Term (PT) only.

- Adverse events collected during the pre-treatment period (see definition in Section 5.5) will be considered pre-treatment and included in listings (marked with a flag).
- Treatment-emergent adverse events (TEAEs) are defined as AEs which begin, or worsen, during the on-treatment period.
- Adverse events collected during post-treatment period may be tabulated separately from the TEAEs and provided in listings (marked with a flag).

The following summaries of TEAEs will be presented:

- TEAE overview
- TEAEs by PT, in order of descending frequency
- TEAE by SOC, PT and Worst Toxicity Grade, in order of descending frequency
- Related TEAEs, by PT, in order of descending frequency
- TEAE Leading to Withdrawal from Treatment by SOC, PT and Worst Toxicity Grade, in order of descending frequency
- Serious TEAEs, by PT, in order of descending frequency
- Fatal TEAEs (TEAEs resulting in death) by PT, in order of descending frequency

9.3 Adverse Events of Special Interest (AESI)

Cytokine Release Syndrome (CRS) events will be graded as per Lee et al 2019 and as described in Section 10.3.1 of the protocol. The summaries include:

• Subjects with at least one CRS Event (by maximum Grade)

- CRS signs and symptoms
- CRS Accompanied by tocilizumab use, leading to dose modification, leading to treatment discontinuation
- Time to first CRS Onset (days)
- Longest CRS Duration (days)

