#### 7 DOSE MODIFICATIONS AND SAFETY MANAGEMENT GUIDELINES

# 7.1 **Dose-Limiting Toxicity**

The DLT evaluation period is defined as the period from the start of the first GEN1044 administration on C1D1 of the Dose Escalation part of the trial until 7 days after the first full dose. As described in Section 4.1, if a subject receives the priming dose on C1D1, one intermediate dose on C1D8, and the full dose starting on C1D15, the DLT period will be the first 21 days of Cycle 1 (Cycle 1 days 1 through 21). If a subject receives the priming dose on C1D1, the first intermediate dose on C1D8, the second intermediate dose on C1D15, and the first full dose on C2D1, the DLT period will be Cycle 1 up to and including C2D7 (ie, a total of 28 days). The DLT evaluation period may be adjusted for potential GEN1044 treatment delay as described in Section 11.1.7.

National Cancer Institute (NCI) Common Terminology Criteria for Adverse Events (CTCAE) v5.0 (NCI-CTCAE, 2017) will be used to assess toxicities/AEs, except for CRS and immune effector cell-associated neurotoxicity syndrome (ICANS) (see Section 10.4.1 and Section 10.4.2, respectively).

A DEC is set up for the study. The DEC will review data from each DL cohort and make a decision regarding dose escalation. That decision of the DEC has to be confirmed by the sponsor SC. The DMC will review data on a quarterly basis.

Events to be collected and assessed by the DMC for DLTs include: SAEs; AESIs where applicable; and clinically significant abnormal laboratory values (that are not already covered by a separate AE term).

The occurrence of any of the toxicities outlined in this section will be considered a DLT if assessed by the investigator to be at least possibly related to GEN1044. AEs clearly not related to the trial treatment (GEN1044) such as disease progression, environmental factors, unrelated trauma, etc, should not be considered a toxicity event.

The following will qualify for a DLT:

- ≥ Grade 3 CRS, graded according to American Society for Transplantation and Cellular Therapy (ASTCT) criteria (Lee et al., 2019) (see Section 10.4.1, Table 16).
- \geq Grade 3 ICANS, graded according to the criteria specified in Table 17, Section 10.4.2.
- Any Grade 3 or 4 non-hematologic toxicity except for:
  - Grade ≥ 3 nausea/vomiting or diarrhea <72 hours with adequate anti-emetic and other supportive care
  - Grade  $\geq$  3 fatigue  $\leq$ 1 week

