#### 10.3 Evaluation of Adverse Events

#### **Severity**

Toxicities will be graded for severity according to the National Cancer Institute's Common Terminology Criteria for Adverse Events (CTCAE), version 5.0 (NCI-CTCAE, 2017) to describe the intensity of AEs, except for CRS (see Section 10.4.1) and ICANS (see Section 10.4.2).

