# 10.4 Adverse Events of Special Interest

The following are considered AESIs:

- CRS, graded according to ASTCT criteria (Lee et al., 2019) (see Table 16).
- ICANS (Lee et al., 2019)

AESIs are to be entered in the eCRF and reported to the Safety CRO within 24 hours if they meet seriousness criteria or just entered in the eCRF within 72 hours if not serious.

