# 10.4.2 Immune Effector Cell-Associated Neurotoxicity Syndrome

ICANS is a complication associated with endothelial cell activation, increased blood-brain-barrier permeability, and influx of elevated cytokines into the cerebrospinal fluid following T-cell activating therapies. Previously, it was considered in aggregate with CRS, but is now treated as a separate entity owing to its distinct timing and response to intervention. Accordingly, it may occur concurrently with CRS or shortly after CRS symptoms subside (but rarely before). Subjects receiving GEN1044 should be monitored for ICANS to facilitate early recognition, grading, and management. Common clinical manifestations include confusion or delirium, expressive aphasia, headache, seizures, and altered level of consciousness, some of which may mimic findings in an elderly hospitalized patient with fever. ICANS will be graded according to the ASTCT grading for ICANS (Table 17), which comprises five neurotoxicity domains including the immune effector cell-associated encephalopathy (ICE) cognitive assessment score (Table 18) (Lee et al., 2019).

Table 17 Diagnosis and Grading of Immune Effector Cell-Associated Neurotoxicity Syndrome in Adults According to ASTCT Criteria

Neurotoxicity Domain	Grade 1	Grade 2	Grade 3	Grade 4	Grade 5
ICE score*	7-9	3-6	0-2	0 (patient is unarousable and unable to perform ICE)	Death due to ICANS in
Depressed level of consciousness †	Awakens spontaneously	Awakens to voice	Awakens only to tactile stimulus	Patient is unarousable or requires vigorous or repetitive tactile stimuli to arouse. Stupor or coma.	which another cause is not the primary factor leading
Seizure	N/A	N/A	Any clinical seizure focal or generalized that resolves rapidly (≤5 min) or nonconvulsive seizures on EEG that resolve with intervention	Life-threatening prolonged seizure (>5 min); or repetitive clinical or electrical seizures without return to baseline in between.	to this outcome
Motor findings ‡	N/A	N/A	N/A	Deep focal motor weakness such as hemiparesis or paraparesis	
Elevated ICP/cerebral edema	N/A	N/A	Focal/local edema on neuroimaging§	Diffuse cerebral edema on neuroimaging; Decerebrate or decorticate posturing; or cranial nerve VI palsy, or papilledema, or Cushing's triad	

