#### 11.5.3.2 Adverse Events

Summary tables for AEs will include only AEs that started or pre-existing AEs that worsened during the on-treatment period, ie, the treatment-emergent adverse events (TEAEs).

The incidence of TEAEs (new or worsening from baseline) will be summarized by system organ class and/or preferred term; intensity (based on grades of NCI-CTCAE version 5.0) for all TEAEs except for CRS (see Section 10.4.1) and for ICANS (see Section 10.4.2); type of TEAE; relationship to trial treatment.

SAEs, non-serious TEAEs, and AESIs during the on-treatment period will be tabulated.

All fatal TEAEs, and all deaths (both on-treatment and post-treatment deaths) will be summarized.

Version: 4.0

All TEAEs, deaths, and SAEs (including those from the pre- and post-treatment periods) will be listed and those collected during the pre-treatment and post-treatment period will be flagged.

Further summaries of TEAEs and AESIs will be specified in the SAP.

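### SAP 9.3 plans AESI summaries for CRS only, although protocol v4.0 names ICANS as a second AESI to be tabulated and graded by ASTCT; SAP 2.1 does not declare the omission

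*SAP*

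**What the plan says.** **Protocol v4.0.** Section 10.4 introduces its list with "The following are considered AESIs" and gives two entries, CRS and ICANS. Section 11.5.3.2, on adverse events in the Dose Escalation part, states "SAEs, non-serious TEAEs, and AESIs during the on-treatment period will be tabulated" and adds "Further summaries of TEAEs and AESIs will be specified in the SAP". Neither sentence is limited to CRS. Section 10.3 applies CTCAE v5.0 to severity "except for CRS (see Section 10.4.1) and ICANS (see Section 10.4.2"), and 11.5.3.2 repeats the exception for the TEAE summaries. Section 10.4.2 names the scale: "ICANS will be graded according to the ASTCT grading for ICANS (Table 17"). Section 7.1 makes ICANS of at least that grade a DLT criterion: "Grade 3 ICANS, graded according to the criteria specified in Table 17, Section 10.4.2".

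**SAP.** Section 1.1 gives protocol v4.0 as one of its bases, alongside v3.0. Section 9.3 states a grading source for CRS and lists five CRS summaries: subjects by maximum grade ("Subjects with at least one CRS Event (by maximum Grade"), signs and symptoms, tocilizumab use with dose modification and discontinuation, time to first onset, and longest duration. Section 9.2 names MedDRA and CTCAE v5.0 and mentions no other scale. Section 2.1 declares one departure from the protocol, that efficacy is listed and not summarised. Section 2.2 explains that the report is abbreviated because of early termination, but keeps the key safety content at the level of a full report.

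**The concern.** Adverse events are a primary endpoint of the escalation part, and AESIs are the events that the sponsor singled out for closer reporting. A programmer who follows the SAP as written would produce AESI output for CRS and none for ICANS. A reader of the report would then have to find ICANS by searching the general preferred-term tables. The worst-grade columns there would carry no statement of which scale applies to it. Because SAP 2.1 is silent, that reader also could not tell a deliberate decision from an oversight.

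**Working it through.** No sample size, power or event count is involved. The check sets the two documents side by side and counts.

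1. **AESIs named and summarised.** Protocol 10.4 names 2 (CRS, ICANS). SAP 9.3 has 5 bullets: 5 on CRS, 0 on ICANS. So 1 of 2 is covered. ICANS is also absent from the SAP abbreviation list.

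2. **Is the omission declared or covered?** SAP 2.1 declares one change, to efficacy. SAP 2.2 shortens efficacy and other sections but not key safety information. Neither covers it.

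3. **Is a scale stated?** Protocol 10.3, 10.4.2 and 11.5.3.2 take ICANS out of CTCAE, and 10.4.2 puts it on ASTCT Table 17. SAP 9.3 restates the exception for CRS. SAP 9.2 lists 7 TEAE summaries, of which 2 show worst toxicity grade (all TEAEs, and TEAEs leading to withdrawal from treatment). For ICANS, neither has a stated scale. This is a missing statement.

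4. **Where ICANS would still appear.**
   - In the SAP 9.2 tables, by preferred term. The table by SOC, preferred term and worst grade covers all grades over the on-treatment period, and SAP 5.1 presents analyses by dose level cohort.
   - In the data listings.
   - In SAP 9.1 ("DLT will be summarized by PT in order of descending frequency using Dose-Determining Analysis Set"), if the event is a DLT. Under protocol 7.1 that means related ICANS of grade 3 or higher in the DLT period, or treatment-related ICANS of any grade that causes discontinuation in Cycle 1.

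5. **What is left missing.** An AESI summary for ICANS, and a statement that its grades are ASTCT grades.

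6. **Ascertainment over time.** The Amendment 3 list of changes adds ICANS as an AESI and adds the ICE score. The amendment summary places only Amendments 1 and 2 before the first enrolment. Protocol 10.2.1 and 10.2.2 have all adverse events recorded whether or not they are AESIs. Mild ICANS may therefore have been under-ascertained in subjects treated before Amendment 3. The documents do not say how many subjects that is.

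7. **Separate minor check, SAP 5.5.** The rule ends the on-treatment period on the 30th day after the last dose. For assessments on or after first dosing, study day = assessment date − first dose date + 1. For a single dose on Day 1, the 30th day after it has study day 30 + 1 = 31. The SAP example stops at Day 30, which is the last dose + 29 days. The example conflicts with the rule by one day.

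**The case against.** The strongest reply is that little is lost. The worst-grade table in SAP 9.2 already runs over all grades and the whole on-treatment period. Protocol 10.2.2 tells sites to record the diagnosis in preference to its symptoms. If ICANS is coded to one preferred term, that table gives nearly what an ICANS table would give. Protocol 11.5.3.2 requires AESIs to be tabulated without specifying a dedicated table. The grading rule is fixed in the protocol, and an SAP based on v4.0 need not repeat it. SAP 1.1 sends layouts and titles to the Data Presentation Specification, which is not available here, and SAP 9.3 introduces its bullets as what the summaries include, so an ICANS table may exist there.

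Much of this stands, and it limits the weight of the point. It does not remove it. The protocol leaves further AESI summaries to the SAP, and the SAP uses that for one AESI only. SAP 9.3 found it necessary to restate the scale for CRS, so silence on ICANS leaves the two treated differently without a reason. Preferred-term tables also depend on a diagnosis having been entered: under protocol 10.2.2, where none is available, each sign is recorded as its own event. Some cases could then be spread over several terms, though that is an inference.

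**Conclusion.** The point holds as a gap between the protocol and the SAP on a primary safety objective: one of two AESIs has no AESI summary, its scale is unstated, and the omission is undeclared. It should be corrected, but it does not put the underlying data at risk. Confidence in the textual omission is high. The effect on results is unknown, because the documents give no ICANS counts and no numbers treated under each protocol version.

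Three stronger readings are tempting and are not supported:

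- **ICANS would disappear from the report.** It would not; the SAP 9.2 tables, the listings and, for qualifying events, SAP 9.1 would still show it.
- **The SAP instructs ICANS to be graded by CTCAE.** It does not say so. Only laboratory results are graded programmatically (SAP 9.5), and the protocol fixes ASTCT for ICANS.
- **A zero in an early cohort means that ICANS was not collected.** All adverse events were to be recorded regardless of AESI status. Under-ascertainment of mild events before ICE scoring is possible; non-collection is not shown. Protocol v3.0 is not available to settle this.

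The conclusion assumes that the Data Presentation Specification does not already contain an ICANS table. If it does, the remaining task is to say so in SAP 9.3 and to state the scale.

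**What to change.** - **SAP 9.3:** add a by-cohort summary of the number and percentage of subjects with at least one ICANS event, by maximum ASTCT grade (protocol Table 17).
- **SAP 9.2:** add one sentence saying that CRS and ICANS are graded by ASTCT in every table that shows grade.
- **Footnote to the ICANS summary:** ICANS as an AESI and ICE scoring were introduced with Amendment 3, so mild events may be under-ascertained in subjects treated earlier. A split by amendment is not needed.
- **Alternative:** if the omission is intended, declare and justify it in SAP 2.1.
- **Separate minor correction, SAP 5.5:** align the example with the rule. Under the SAP's own study-day formula a last dose on Day 1 gives a period through Day 31. At most, events starting or worsening on that one day are affected, and none are if the rule is what is programmed.

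The cost is one table, one footnote and a few wording edits. For subjects treated under v4.0 the inputs are already required: protocol 10.4 has AESIs entered in the eCRF, and protocol Table 1 schedules the ICE score at five visits (screening, C1D1, C1D8, C1D15 and C2D1). For subjects treated earlier, the entries may rest on general adverse event reports. No new data collection is needed.

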9.4 Death

The number and percentage of subjects died on study, death within 30 Days of last dose, death within 60 days of last dose, as well the number and percentage of subjects died due to each primary cause will be summarized.

9.5 Clinical laboratory results

Haematology and chemistry laboratory results will be graded programmatically using CTCAE 5.0.

The shift of CTCAE grade from baseline to the worst post-baseline grade will be summarized. If a test includes both Hyper- and Hypo- abnormal, then both CTCAE grades will be included in the summaries.

10 Cytokine and immunophenotyping measures

The absolute value of Cytokine, fold change from baseline of Immunophenotyping immune cell margination, and percentage change from baseline of Immunophenotyping T-cell activation will be summarized using descriptive statistics (mean, median, minimum, maximum, n, and standard deviation). Data will be summarized per planned time point during Cycle 1 only.

11 Treatment Response

The timepoint response is evaluated by investigator or qualified designee based on Imaging assessments using Response Evaluation Criteria in Solid Tumours (RECIST) v1.1. The response data will be listed.

12 Software

The data will be analysed using SAS version 9.4 or higher.

13 Abbreviations

ADA	Anti-Drug Antibodies
AE	Adverse Event
AESI	Adverse Event of Special Interest
BMI	Body Mass Index
CI	Confidence Interval
CRF	Case Report Form
CRS	Cytokine Release Syndrome
CTCAE	Common Terminology Criteria for Adverse Events
DDS	Dose-Determining Analysis Set
DLT	Dose Limiting Toxicity
DMC	Data Monitoring Committee
DPS	Data Presentation Specification
ECG	Electrocardiogram
ECOG	Eastern Cooperative Oncology Group
FAS	Full analysis set
IRR	Infusion-Related Reaction
mBOIN	Modified Bayesian Optimal Interval
MedDRA	Medical Dictionary for Regulatory Activities
NSCLC	Non-Small Cell Lung Cancer
NE	Not Estimable
PD	Progressive Disease
PD-1	Programmed Cell Death Protein 1
PD-L1	Programmed Death-Ligand 1
РТ	Preferred Term
RECIST	Response Evaluation Criteria in Solid Tumors
RP2D	Recommend Phase 2 Dose
SAE	Serious Adverse Event
SAF	Safety analysis set
SAP	Statistical Analysis Plan
SCCHN	Squamous Cell Carcinoma of the Head and Neck
SD	Stable Disease
SOC	System Organ Class
TEAE	Treatment Emergent Adverse Event
TNBC	Triple-Negative Breast Cancer
TTNT	Time to Next Anti-Cancer Therapy
WHODRUG	World Health Organization Drug Dictionary

14 References

